### 9.3.3 Covariate Assessment

*Not applicable*

### 9.3.4 Validity and Reliability

*Not applicable*

## 9.4 Data Sources

Data will be provided by study site staff, **utilizing** subject medical notes to abstract information in order to complete electronic CRFs in the study-specific electronic database, which will be provided by the sponsor.

## 9.5 Study Size

Generally the impact of treatments on cancer patients' QoL is explored in clinical studies as a marginal aspect: data are not collected systematically and no longitudinal information are available about this aspect. So, no evidence of outcomes is present in literature.

For the above reasons the study sample size is not based on mathematical or hypothesis evaluations, or power estimation, but on feasibility considerations.

- Expected number of subjects presenting selected diseases and respecting inclusion/exclusion criteria
- Enrolment capacity and management of patients from centers
- Number of patients with the same disease enrolled in other studies, and their mean follow up time observed

A total sample size of 300 patients has been planned for this study: it is estimated that about 50% (150 pts) of them should be able to complete the QoL questionnaires during the whole treatment period. This population is estimated relevant from the scientific board and useful for a first evaluation on variability of QoL during the whole treatment period.

## 9.6 Data Management

Data are abstracted by site staff from subject notes into an electronic database provided by the sponsor. The sponsor provides protocol-specific training to all site staff delegated to abstract subject data. An eCRF Completion Guideline is provided.

The Amgen representative(s) and regulatory authority inspectors are responsible for contacting and visiting the Investigator for the purpose of inspecting the facilities and, upon request, inspecting the various records of the clinical study (eg, CRFs and other pertinent data) provided that subject confidentiality is respected.

The Clinical Monitor or designee is responsible for verifying the CRFs at regular intervals throughout the study to verify adherence to the protocol completeness, accuracy, and consistency of the data; and adherence to local regulations on the conduct of research.

The Clinical Monitor, or designee is to have access to subject medical records and other study-related records needed to verify the entries on the CRFs in accordance with the local laws and regulations.

The Investigator agrees to cooperate with the Clinical Monitor, or designee to ensure that any problems detected in the course of these monitoring visits, including delays in completing CRFs, are resolved

**9.6.1 Obtaining Data Files**

Not applicable

**9.6.2 Linking Data Files**

Not applicable

**9.6.3 Review and Verification of Data Quality**

Automatic edit checks within the database and further manual review by the sponsor help to ensure quality and completeness of the data. Data queries are sent to site for clarification and resolution of discrepancies.

**9.7 Data Analysis**

**9.7.1 Planned Analyses**

**9.7.1.1 Primary Analysis**

The primary analysis will be conducted at the end of the study.

**9.7.2 Planned Method of Analysis**

**Outcome Variable(s):**

- HRQoL will be measured using the EORTC QLQ-C30 questionnaire. EORTC QLQ-C30 scores reported during the treatment will be also expressed as percentage of the scores reported at baseline.
- Skin satisfaction will be measured using the DLQI. The DLQI score will also be expressed as a percentage of the maximum possible score of 30. DLQI scores reported during the treatment will be also expressed as percentage of the DLQI scores reported at baseline.

Approved

- Tolerability: The toxicity rate, defined as the percentage of patients, relative to the total of enrolled subjects, experiencing a specific adverse event of any grade, according to National Cancer Institute Common Toxicity Criteria (NCI CTC-AE version 4.0), will be reported. Times to onset of dermatological toxicities will be also described.
- Management of dermatological toxicity: concomitant medications, both topical and systemic, adopted to prevent or treat dermatological adverse events will be recorded.

### **Exposure Variable(s)**

Treatment adherence: The percentage of delayed cycles, the percentage of cycles administered with reduced doses, the number of administered cycles, the median treatment duration and the average relative dose intensity of every planned drug will be reported.

#### **9.7.2.1 General Considerations**

All recorded parameters will be described: absolute frequency and percentage will be calculated for qualitative variables, while mean, standard deviation, median, first and third quartile will be used to summarize quantitative variables.

The population will be analyzed totally and stratified for treatment (FOLFOX plus panitumumab and FOLFOX plus cetuximab).

The level of significance will be set to  $p < 0.05$ . No interim analyses are planned for this study.

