## 9. Research Methods

### 9.1 Study Design

This is a national, multicentric, prospective, observational trial. The decision to prescribe FOLFOX or FOLFIRI plus panitumumab or FOLFOX or FOLFIRI plus cetuximab must have been freely taken by the clinician prior to the study entry for each patient included. Each physician will see his/her patients within the context of routine visits, without any special visit being organized for the purposes of the study. Therefore, the doctor-patient relationship and patient follow-up are not modified. Physicians are totally free to decide on their patients' therapeutic management.

EORTC QLQ-C30 and DLQI questionnaires will be completed by the patients at baseline (Day 1 of Cycle 1), at the first day of every other cycle (every 2 weeks) thereafter, and at "End of Study Visit" (within 28 days from the end of treatment with anti-EGFR or withdrawal from study for any reason).

Before every cycle, adverse events will be recorded and graded according to NCI CTCAE Version 4.0. Treatment's modifications in terms of cycles' delay, dose reductions or drugs' interruptions will be recorded. Concomitant approaches to prevent or treat dermatological toxicities during the treatment will be registered.

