**Baseline**

- Physical examination: ECOG, weight and height
- Prevention of cutaneous toxicity: yes vs no
- Magnesium levels
- Concomitant medications
- AE/SAE
- Administered treatment: administered chemotherapy, administered anti-EGFR and anti-EGFR modifications
- Dermatology Life Quality Index (DLQI) questionnaire
- EORTC QLQ-C30

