### 9.3.2 Outcome Assessment

HRQoL will be measured using the EORTC QLQ-C30 questionnaire. The EORTC QLQ-C30 includes 5 functional scales (physical, role, emotional, social, and cognitive functioning), 3 symptom scales (fatigue, pain, and nausea and vomiting), a global health status scale, and a number of single items assessing additional symptoms (dyspnea, sleep disturbances, constipation, and diarrhea), and perceived financial impact. For the majority of the EORTC QLQ-C30 items a 4-point Likert-type response scale is used. The only exception is the global health status/QoL scale in which a 7-point Likert-type scale is used. For ease of interpretation, all scales and individual item responses are linearly converted to a 0 to 100 scale. EORTC QLQ-C30 scores reported during the treatment will be also expressed as percentage of the scores reported at baseline.

Skin satisfaction will be measured using the Dermatology Life Quality Index (DLQI). The DLQI questionnaire includes 10 questions scored from 0 (not at all, not relevant, not answered) to 3 (very much). The DLQI score is calculated by summing the scores of each question resulting in a minimum of 0 and a maximum of 30. A higher score means an impairment of the quality of life. The DLQI score will also be expressed as a percentage of the maximum possible score of 30. DLQI scores reported during the treatment will be also expressed as percentage of the DLQI scores reported at baseline.

Tolerability: The toxicity rate, defined as the percentage of patients, relative to the total of enrolled subjects, experiencing a specific adverse event of any grade, according to National Cancer Institute Common Toxicity Criteria (NCI CTC-AE version 4.02 ), will be reported. Times to onset of dermatological toxicities will be also described.

Treatment adherence: The percentage of delayed cycles, the percentage of cycles administered with reduced doses, the number of administered cycles, the median treatment duration and the average relative dose intensity of every planned drug will be reported.

Management of dermatological toxicity: concomitant medications, both topical and systemic, adopted to prevent or treat dermatological adverse events will be recorded.

Approved

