## 11. Collection, Recording, and Reporting of Safety Information and Product Complaints

### 11.1 Definition of Safety Events

#### 11.1.1 Adverse Events

An adverse event is any untoward medical occurrence in a subject/patient administered a pharmaceutical product(s) irrespective of a causal relationship with this treatment.

An adverse event can therefore be any unfavorable and unintended sign (including an abnormal laboratory finding, for example), symptom, or disease temporally associated with the use of a product(s), whether or not considered related to the product(s). The definition of an adverse event includes:

- Worsening of a pre-existing condition or underlying disease
- Events associated with the discontinuation of the use of a product(s), (eg, appearance of new symptoms)

It is the investigator's responsibility to evaluate whether an adverse event is related to an Amgen product prior to reporting the adverse event to Amgen.

An adverse device effect is any adverse event related to the use of a combination product or medical device. Adverse device effects include adverse events resulting from insufficient or inadequate instructions for use, adverse events resulting from any malfunction of the device, or adverse events resulting from use error or from intentional misuse of the device.

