### 11.2 Safety Collection, Recording and Submission to Amgen Requirements

**This study is prospectively collecting information of enrolled patients. All safety events (adverse events, product complaints, and other safety findings) considered to have occurred following subject exposure to anti-EGFR will be collected from signing of the informed consent form to the final study contact. The investigator is responsible for recording safety events that they become aware of during study period in the patient's appropriate documentation.**

**Collected safety events occurred after subject exposure to panitumumab, with the exception of the protocol-exempted events listed in the section below, must be**

**submitted as individual safety reports to Amgen via the applicable Amgen Safety Reporting Form (paper form) within 1 business day of investigator awareness.**

See [Appendix B](#) for sample Safety Report Form(s), [Appendix C](#) for Additional Safety Reporting Information regarding the adverse event grading scale used in this study, and [Appendix D](#) for sample Pregnancy and Lactation Notification Worksheets.

The Investigator may be asked to provide additional information for any event submitted, which may include a discharge summary or extracts from the medical record.

Information provided about the event must be consistent with information recorded **in the study documentation** where safety data may also be recorded (eg.: **Case Report Form, CRF**).

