#### **11.2.1 Protocol Exempted Safety Information**

**Regardless of causality, for this study all safety events experienced by the subjects exposed to panitumumab must be reported to Amgen within 1 business day of investigator awareness with the exception of the following non serious adverse events related to anti-EGFR and induced by chemotherapy as listed below:**

- **Non serious adverse events related to anti-EGFR (Vectibix®): skin and nails disorders and hypomagnesemia.**
- **Non serious adverse events induced by chemotherapy: anemia, neutropenia, neurotoxicity, diarrhea.**

**The rationale for exempting the above non serious events from reporting to Amgen within 1 business day is that the safety profile of panitumumab, and chemotherapies are fully described in the respective Summary of Product Characteristics.**

If any of the exempted events have a fatal outcome, they should be considered a serious adverse event and must be reported individually within 1 business day of investigator awareness.

All safety information that is not specified in this section including all fatal events are to be collected and submitted to Amgen within the specified time frame.

**Protocol-exempted events and safety events that are suspected to be related to any medicinal product other than panitumumab should be reported to the local authority in line with the local country requirements.**

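### Hypomagnesaemia may be under-ascertained: magnesium is measured throughout, but no patient-level grade is derived from it and the rate rests on investigator-entered events

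*Combined protocol and SAP*

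**What the plan says.** **Collection.** Section 9.3 lists "Magnesium levels" at baseline and again at the repeatable study visit and the End of Study Visit. Table 1 agrees. It is the only laboratory test named in that schedule.

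**Analysis of the values.** Neither section 9.7.2 (outcome variables) nor section 9.7.2.4 (endpoint analyses) mentions magnesium, and section 9.7.3 (safety analysis) is marked not applicable. What remains is the general rule in section 9.7.2.1: "mean, standard deviation, median, first and third quartile will be used to summarize quantitative variables".

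**Tolerability.** Section 9.3.2 defines the toxicity rate as the percentage of enrolled subjects "experiencing a specific adverse event of any grade, according to National Cancer Institute Common Toxicity Criteria". Section 9.7.2.4 also relates the number of events to the anti-EGFR drug by ANOVA.

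**How events enter the record.** Section 9.1: "Before every cycle, adverse events will be recorded and graded according to NCI CTCAE Version 4.0". Section 11.1.1 defines an adverse event to cover "any unfavorable and unintended sign (including an abnormal laboratory finding, for example), symptom, or disease". Section 11.2: "The investigator is responsible for recording safety events that they become aware of during study period".

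**Hypomagnesaemia.** Section 11.2.1 names "skin and nails disorders and hypomagnesemia" as the non-serious anti-EGFR-related events exempt from one-business-day reporting to the sponsor.

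**The concern.** Assessing tolerability is a secondary objective. For a laboratory toxicity, the useful results are how many patients became low and how low each one went. The plan collects serial values that could answer this but gives them no patient-level use: no worst value, no proportion below the limit, no CTCAE grade and no shift from baseline. The rate that will be reported comes from event entry alone.

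Event entry depends on someone at the site noticing the result and judging it to be an event. Section 11.1.1 allows an abnormal laboratory finding to count, but no section says when a low magnesium value must be entered. Skin toxicity has its own collection item at each study visit; hypomagnesaemia has none. With about 33 centres, practice may differ. If it differs between centres that favour one drug and centres that favour the other, the difference passes into the event-by-drug comparison in section 9.7.2.4.

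**Working it through.** **Is there a figure to reproduce?** No. The documents give no expected incidence, threshold or power for magnesium. The only arithmetic in section 9.5 is 300 × 50% = 150 questionnaire completers. It is correct, but has no bearing here.

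**Step 1: can the planned summaries give a patient count?** They are cross-sectional and do not link visits within a patient. Suppose (assumption) 5% of patients are low at each of six visits. The share ever low is:
- 5% if they are always the same patients;
- 1 − 0.95^6 = 26.5% if visits are independent;
- 6 × 5% = 30% if no patient is low twice.

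The same visit-level figures fit all three. At 5% per visit, the first quartile does not reach the low values either.

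**Step 2: do the summaries conceal a large shift?** Not necessarily. Suppose (assumptions) 30% of patients fall by 0.3 mmol/L from a baseline mean of 0.85 mmol/L with SD 0.05 to 0.12, and the rest do not change.
- Mean change: 0.30 × 0.3 = 0.09 mmol/L.
- SD afterwards: √(SD² + 0.3 × 0.7 × 0.3²). For 0.05 this is √0.0214 = 0.15; for 0.12 it is √0.0333 = 0.18.
- First quartile: because 30% exceeds 25%, it lies within the affected group and falls by about 0.14 to 0.22 mmol/L.

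So the planned statistics would show that something happened, but not how many patients were affected or at what grade.

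**Step 3: how large could under-ascertainment be?** Let p be the true any-grade incidence and s the share of affected patients entered as events. Both are assumptions; neither is in the documents. On 300 enrolled, reported = 300 × p × s and missed = 300 × p × (1 − s).

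| p (patients) | s = 100% | s = 90% | s = 70% | s = 50% |
|---|---|---|---|---|
| 10% (30) | 30, missed 0 | 27, missed 3 | 21, missed 9 | 15, missed 15 |
| 20% (60) | 60, missed 0 | 54, missed 6 | 42, missed 18 | 30, missed 30 |
| 30% (90) | 90, missed 0 | 81, missed 9 | 63, missed 27 | 45, missed 45 |
| 40% (120) | 120, missed 0 | 108, missed 12 | 84, missed 36 | 60, missed 60 |

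The range is 3 to 60 patients for s between 90% and 50%, and zero for s = 100%.

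**Step 4: the drug comparison.** If both drugs had a true rate of 20%, but entry were 90% with one and 70% with the other (assumptions), the reported rates would be 0.20 × 0.90 = 18% and 0.20 × 0.70 = 14%. That is a 4-point difference produced by entry alone.

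**The case against.** The strongest reply is that the protocol already closes the gap if it is followed. Magnesium and adverse events are scheduled at the same visits, events are recorded and graded before every cycle, and the definition expressly includes laboratory abnormalities. Section 9.6 has a monitor checking the case report forms for completeness, and section 9.6.3 adds edit checks and manual review. This stands as far as it goes: under-counting is a risk, not a demonstrated error. It does not remove the risk, because no section links a low value to an event entry and section 11.2 ties recording to investigator awareness.

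A reader might go further in four ways that the documents do not support:

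- *That hypomagnesaemia is under-counted as a matter of fact.* The share of low values entered is not given and could be 100%.
- *That the plan merely averages magnesium and so hides affected patients.* SD, median and quartiles are also planned, and Step 2 shows that they can move visibly.
- *That the exemption in section 11.2.1 leaves the event entry as the only record.* The exemption concerns rapid reporting to the sponsor. The events are still collected under section 11.2, exempted events are directed to the local authority, and the magnesium values and concomitant medications are recorded as well.
- *That this is a toxicity to which the protocol gives special weight.* Section 7.2 reserves special interest for dermatological events. Section 11.2.1 shows only that hypomagnesaemia is recognised as related to anti-EGFR treatment.

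It is also fair to say that the data needed for grading are not shown to be complete. Units and laboratory limits are not listed as collected, visits follow routine care, and section 9.7.2.2 rules out imputation.

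**Conclusion.** The point holds as a gap in the plan. Serial magnesium values are collected and only generic descriptive statistics are planned for them, so the incidence and grade of hypomagnesaemia rest on event entry and may be under-ascertained, possibly unevenly by site or drug. The documents do not fix the size. The 3 to 60 of 300 patients above follows wholly from the assumed incidence and entry shares, and is zero under full entry. The point affects a secondary objective and the event-by-drug comparison, not the primary quality-of-life analysis. It is a worthwhile improvement rather than a defect that threatens the study.

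**What to change.** Keep the event-based toxicity rate on enrolled subjects, so that hypomagnesaemia stays comparable with every other event in the same table. In section 9.7.2.4 add one table derived from the scheduled values:

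- worst post-baseline CTCAE v4.0 magnesium grade per patient, as any grade and grade 3 or more;
- shift from baseline grade to worst post-baseline grade;
- both overall and by anti-EGFR drug;
- the reported hypomagnesaemia events alongside;
- the number of patients with at least one post-baseline value, because this denominator will differ from the number enrolled.

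Describe recorded magnesium supplementation, but do not split the results by it: supplementation may be a response to a low value, so the split would be hard to interpret. Do not merge the two sources into a single laboratory-or-event count, which would make this rate unlike the others.

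**Cost.** One derived variable and one table, with no new patient procedures. Units and each site's laboratory limits must be confirmed or collected; where limits cannot be obtained, restrict the table to grades defined by absolute cut-offs. The laboratory-based rate may be higher than the reported one, and the report should say why the two differ.

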#### 7.1 Diseases and Therapeutic Area

Different options are currently available as upfront choices for the systemic treatment of metastatic colorectal cancer patients. In the last years different phase III trials investigated the addition of a drug targeting the Epidermal Growth Factor Receptor (anti- EGFR) to a first-line chemotherapy doublet, leading to the approval of two anti-EGFR monoclonal antibodies: the chimeric human-murine IgG1 cetuximab and the fully human IgG2 panitumumab.

The prospective and *post-hoc* analyses of randomized trials of first-line chemotherapy with or without an anti-EGFR monoclonal antibody, show that patients bearing a mutation in *KRAS* codon 12 or 13 do not benefit from the addition of the anti-EGFR to the upfront chemotherapy doublet, so that the use of both cetuximab and panitumumab has been restricted to *KRAS* wild-type patients. More recently, a pre-specified analysis of results of the PRIME trial showed for the first time that also patients bearing a mutation in some hotspots of *KRAS* (other than codon 12 and 13) and *NRAS* genes (ie, codon 12, 13, 59, 61, 117 and 146) do not achieve benefit from the addition of cetuximab or panitumumab to first-line chemotherapy. A potential detrimental effect of adding anti-EGFRs to first-line FOLFOX was also suggested in mutated patients. On the other hand, the efficacy of anti-EGFR monoclonal antibodies was optimized in patients not bearing any mutation in *KRAS* or *NRAS* codon 12, 13, 59, 61, 117 and 146, defined as *RAS* wild-type patients. Based on these results, the European Medicines Agency further

restricted the use of both panitumumab and cetuximab to this subgroup of patients. In March 2015, the European Medicines Agency approved the extension of indication for Panitumumab FOLFIRI in 1st line. The new indication was implemented by Italian Medicines Agency on 24 February 2017.

Therefore doublet plus panitumumab or cetuximab are valuable options for the upfront treatment of *RAS* wild-type mCRC patients.

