## 9.2.3 Subject/Patient/Healthcare Professional Eligibility

### 9.2.3.1 Inclusion Criteria

Adult ( $\geq$  18 years old) RAS wild-type metastatic colorectal cancer patients candidate to receive FOLFOX or FOLFIRI plus panitumumab or FOLFOX or FOLFIRI plus cetuximab as upfront treatment as per clinical practice.

Willingness and ability to comply with the protocol.

Written informed consent to study procedures.

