#### **9.7.2.4 Analysis of the Primary, Secondary, and Exploratory Endpoint(s)**

To reach the primary endpoint ("To assess the impact of the treatment with FOLFOX or FOLFIRI plus anti-EGFR MAbs on patients' health related quality of life"), comparison between the QoL scores (total and partials) at different times will be done and

differences in mean from basal and follow-up times will be tested with T-test (Student T-test) paired data.

EORTC-QLQ C30 score will be calculated in the total population and also in the two subgroups: FOLFOX/FOLFIRI plus panitumumab and FOLFOX/FOLFIRI plus cetuximab.

Differences in mean between the two subpopulation will be tested at different times with T-test.

- To investigate the impact of dermatological adverse events during the treatment with FOLFOX or FOLFIRI plus anti-EGFR MABs on patients' skin satisfaction will be calculated the Dermatology Life Quality Index (DLQI) score.

Differences in mean between the two subpopulation will be tested at different times with T-test.

- To assess the tolerability of administered treatments, Tolerability and compliance to treatments will be described. Their effect on QoL will be evaluated with a multivariate analysis (Anova).
- To describe the adherence to the treatment **with antiEGFR** in terms of dose delays, dose reductions, number of administered cycles, average relative dose intensity of every drug, all these parameters will be described and the single values observed will be compared with the values reported previously, to determine variations .
- Every adverse event occurred will be described with particular attention to dermatologic ones: description, severity and management of the event will be illustrated. Correlation with number of event and treatments (FOLFOX/FOLFIRI plus panitumumab and FOLFOX/FOLFIRI plus cetuximab) will be verify with a multivariate analysis (Anova)
- Will be verified the presence of preemptive treatment of skin toxicities, and events of skin toxicities . The correlation between events of skin toxicities, QoL and presence of preemptive treatment will be tested with a multivariate analysis (Logistic)

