#### **9.7.2.5.2 Stratified Analysis**

Not applicable

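### The general stratification rule in Section 9.7.2.1 names only the two FOLFOX regimens, so FOLFIRI patients belong to no stratum, contrary to the subgroups in Section 9.7.2.4

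*Combined protocol and SAP*

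**What the plan says.** - **Eligibility (Section 9.2.3.1).** Patients are candidates for "FOLFOX or FOLFIRI plus panitumumab or FOLFOX or FOLFIRI plus cetuximab as upfront treatment". That is four regimens. The primary objective in Section 8.1 likewise covers both backbones.
- **General analysis rule (Section 9.7.2.1).** The population is analysed as a whole and "stratified for treatment (FOLFOX plus panitumumab and FOLFOX plus cetuximab"). Both named strata have a FOLFOX backbone.
- **Endpoint analyses (Section 9.7.2.4).** The QLQ-C30 score is calculated overall and "in the two subgroups: FOLFOX/FOLFIRI plus panitumumab and FOLFOX/FOLFIRI plus cetuximab". Means in the two subpopulations are then compared by t-test at each time. The adverse event analysis uses the same grouping: "Correlation with number of event and treatments (FOLFOX/FOLFIRI plus panitumumab and FOLFOX/FOLFIRI plus cetuximab").
- **Status of the text.** Neither list of amendment changes (Section 5, and the summary of changes at the end of the document) has an entry for Section 9.7.2.1, so its FOLFOX-only wording is current.
- **Regulatory background (Section 7.1).** On panitumumab with FOLFIRI in first line: "The new indication was implemented by Italian Medicines Agency on 24 February 2017".

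**The concern.** Section 9.7.2.1 is the general rule for describing all recorded parameters. A programmer who follows it would produce stratified tables with no place for FOLFIRI patients, while one who follows Section 9.7.2.4 would include them. Both would be following the plan, and their tables would rest on different populations. If the choice is left until the data are in hand, it becomes a post hoc choice.

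A second, smaller issue appears once the groups are aligned. Section 9.7.2.4 then compares panitumumab with cetuximab by unadjusted t-tests in groups that pool the two backbones. Treatment is freely chosen by the clinician (Section 9.1), so the backbone mix may differ between antibodies. Part of an apparent antibody difference could then be a backbone difference.

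**Working it through.** **The plan's own figure.** Section 9.5 plans 300 patients and expects about 50% to complete the questionnaires throughout: 300 × 0.50 = 150, which agrees with the plan. The 300 rests on feasibility and has no power formula to reproduce.

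**Coverage of the regimens, side by side.**

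| Regimen | Eligible (9.2.3.1) | In a 9.7.2.1 stratum | In a 9.7.2.4 subgroup |
|---|---|---|---|
| FOLFOX + panitumumab | yes | yes | yes |
| FOLFOX + cetuximab | yes | yes | yes |
| FOLFIRI + panitumumab | yes | no | yes |
| FOLFIRI + cetuximab | yes | no | yes |
| Regimens covered | 4 | 2 | 4 |

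**How many patients this could touch.** The documents do not give the FOLFIRI share, so call it *f* and treat it as an assumption.

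- Patients in no stratum = 300 × *f*
- Patients in a stratum = 300 × (1 − *f*)
- Expected completers in a stratum = 150 × (1 − *f*), if completion does not depend on backbone

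| Assumed *f* | In no stratum | In a stratum | Completers in a stratum |
|---|---|---|---|
| 20% | 60 | 240 | 120 |
| 40% | 120 | 180 | 90 |
| 60% | 180 | 120 | 60 |

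With the Section 9.7.2.4 grouping, all 300 patients and all 150 expected completers fall in a group, whatever *f* is.

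**Why backbone may be unbalanced.** Enrolment starts in about November 2015 and lasts about 50 months (Section 9.2.1). From 1 November 2015 to 24 February 2017 is about 15.8 months, and 15.8 / 50 = 32% of the enrolment period. During that time panitumumab with FOLFIRI was not yet an implemented Italian indication.

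**Why backbone could matter to the outcomes.** Section 11.2.1 attributes anemia, neutropenia, neurotoxicity and diarrhea to chemotherapy. Diarrhea is also a QLQ-C30 item (Section 9.3.2). The documents do not say that these effects differ between FOLFOX and FOLFIRI, so this shows that confounding by backbone is plausible, not that it is present.

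**The case against.** The strongest reply is that this is one outdated parenthesis with limited effect. Section 9.7.2.4 covers all four regimens and says so twice, and a specific endpoint rule would normally prevail over a general remark. No listed objective is a comparison of the antibodies, and Section 7.3 calls the analyses descriptive only. Much of this stands: the primary analysis is not harmed. It does not remove the defect, because nothing in the plan says which section prevails, and Section 9.7.2.4 still plans between-antibody tests.

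A reader might also infer more than the documents support:

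- **That FOLFIRI patients drop out of the study's analysis.** They do not. Section 9.7.2.1 also analyses the whole population, and the primary paired t-tests are run there.
- **That the antibody comparisons lose precision.** A factor of 1/√(1 − *f*) gives standard errors larger by 12%, 29% or 58% at *f* = 20%, 40% or 60%. It would apply only if the FOLFOX-only strata were used for the comparison, and with the same FOLFIRI share under both antibodies. The tests in Section 9.7.2.4 use groups that include FOLFIRI.
- **That the backbone mix cannot be balanced between antibodies.** One implementation date does not show this. The same section dates the European approval to March 2015, before enrolment. The document does not show which regimens were eligible before the May 2017 amendment, and 32% of the months is not 32% of the patients.
- **That the eligibility criteria are contradicted.** They define who enters; Section 9.7.2.1 defines a breakdown. Against eligibility the fault is incomplete coverage. The direct conflict is with Section 9.7.2.4.
- **That the entry under "Stratified Analysis" (Section 9.7.2.5.2) must change.** It is marked not applicable, but it sits under Sensitivity Analysis and can mean only that no stratified sensitivity analysis is planned.

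**Conclusion.** The inconsistency is real, and the wording needs correcting before analysis. Section 9.7.2.1 covers two of the four eligible regimens and conflicts with the subgroups in Section 9.7.2.4. Its reach is the stratified summaries under a literal reading: 60 to 180 of 300 patients in no stratum for assumed FOLFIRI shares of 20% to 60%. No figure stated in the plan changes, and the total-population results are unaffected. The coverage finding rests on the text alone; only the patient counts depend on the assumed share.

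Confounding of the antibody comparison by backbone is possible but not demonstrated. It justifies a cheap adjustment. It does not justify a mandatory split into four strata: with about 150 expected completers, four cells would average 150 / 4 = 37.5 patients before any imbalance.

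**What to change.** **Required.** Rewrite the parenthesis in Section 9.7.2.1 so that the strata match Section 9.7.2.4: "FOLFOX/FOLFIRI plus panitumumab and FOLFOX/FOLFIRI plus cetuximab". Every enrolled patient then belongs to a stratum, and the strata add up to the total. The cost is one line of wording.

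**Recommended.** In Section 9.7.2.4, replace the unadjusted between-antibody t-tests with comparisons adjusted for backbone, for example a linear model at each time with antibody and backbone as terms. Show descriptive results by backbone where cell sizes allow, under a rule for sparse cells set in advance. No new data are needed: Section 9.3 already records the first-line schedule and the anti-EGFR at screening, and the administered chemotherapy and anti-EGFR at baseline and study visits. The cost is slightly more analysis and some small cells.
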